## 4.5 Retrospective Cohort Study Objectives and End-points

#### 4.5.1 Retrospective Cohort Study Objectives

The primary objective is to determine more precisely the rate of transition to MPM in patients diagnosed with BAPE.

The secondary objective is to identify baseline predictors of transition to MPM, allowing refinement of the current Meso-ORIGINS eligibility criteria

### 4.5.2 Retrospective Cohort Study End-points

The **Primary End-Point** shall be the rate of MPM transition, defined as the number of eligible patients diagnosed with MPM within 2 years of the index diagnosis of BAPE divided by the total number of eligible patients.

The **Secondary End-Point** shall be a logistic regression model for MPM transition using baseline data as predictors.

#### 4.6 Trial Flow Chart – Prospective Feasibility Study

\*\* Provide another opportunity for patients to provide consent if required

\*\*\* Can occur as early as 2 month following biopsy if symptomatic recurrence of pleural effusion or any other manifestation of progressive ipsilateral pleural disease. If patient recruited  $\geq$ 6months after initial BAPE diagnosis, then visit 1 and 2 can be combined at day 0.

## 5.1 Scientific Background

#### 5.1.1 Introduction

MPM is an invasive thoracic malignancy associated with prior asbestos exposure. It typically develops 30-50 years after inhalation of asbestos fibres and frequently presents with breathlessness resulting from a pleural effusion. Median survival is poor at 9.5 months, and is principally determined by performance status and histological subtype. (10) Despite recent improvement in the resources available for the management of MPM, the disease remains universally fatal and there has only been a modest improvement in survival rates. (11)

### 5.1.2 Diagnosis of Incident MPM

Contrast enhanced computed tomography (CT) remains the key radiological investigation for suspected pleural malignancy (PM), including MPM. (12) Features of pleural malignancy visible on CT include more than one centimetre of pleural thickening, nodular or mediastinal pleural thickening, inter-lobar fissural modularity and infiltration of the chest wall or diaphragm (13, 14). However, results from a recent study suggested that almost half of patients with an eventual diagnosis of pleural malignancy have a benign CT. (15) Therefore, a benign CT report should not be used alone in confirming a non-malignant diagnosis.

The diagnostic yield of fluid cytology in malignant pleural effusion is approximately 60%, varying by tumour type (12). However, this is significantly lower in MPM, due to the bland cytological appearance of MPM cells, making it difficult to differentiate MPM from benign reactive mesothelial proliferation. This is reflected in the recommendations made in the recent BTS guidelines for MPM, which recommends histological confirmation of all cases. (16)

Local Anaesthetic Thoracoscopy (LAT) allows direct visualisation of abnormal areas of pleura, multiple biopsies to be taken and provision of definitive pleural effusion management, e.g. pleurodesis, within a single procedure. LAT is well-tolerated and can be performed as a day-case. It offers high diagnostic sensitivity (MPM sensitivity 92.6%, specificity 100% n=1369 cases) and is associated with a low complication rate (0% mortality in over 2000 diagnostic LAT cases across 28 studies and a 1.8% major complication rate in over 4500 LAT cases across 47 studies). (17)

Thoracic ultrasound (TUS) is necessary to assess the pleural space characteristics prior to LAT. During respiration, the parietal pleural slides on the visceral pleural, producing the 'sliding sign'. This would not be present if there was pleural adherence, previous pneumothorax or previous pleurodesis. Therefore, the presence of the 'sliding sign' can be used to assess LAT feasibility. TUS can also identify potential challenges to thoracoscopy such as pleural thickening and septation. (8) In cases where LAT is not feasible because either the patient is frail, pleural fluid is heavily located, or where the lung is adherent to the chest wall, TUS-directed cutting pleural biopsy should be considered as an alternative (9).

#### 5.1.3 Benign Asbestos-related Pleural Effusion

Patients with suspected pleural malignancy are frequently found to have non-specific pleuritis/pleural fibrosis at LAT or image guided biopsy. When associated with prior asbestos exposure, these patients are given the label of 'Benign Asbestos-related Pleural Effusion (BAPE)'. A retrospective, single-centre study of 142 LAT patients reported BAPE in 31% of patients, of whom12% (95% CI 4.5% - 26.4%) subsequently developed MPM over 2 years of follow-up (2). Consequently, patients with BAPE are routinely followed up in pleural clinics and repeat biopsies pursued if pleural effusion recurs or there are other indicators of MPM.

Benign asbestos-related pleural effusion (BAPE) is one cause of non-specific pleuritis. Although this syndrome was initially described in 1964 (18), the true nature and outcome of these patients has been poorly studied. In particular, it is not clear whether BAPE is a genuine precursor of MPM in some patients, or simply a reflection of false negative biopsies in a minority of patients with thoracoscopically occult MPM. Alternatively, BAPE could reflect an unrelated inflammatory episode that promotes MPM via the pro-angiogenic and immunosuppressive factors known to exist within pleural effusion (19). Whatever the mechanism, BAPE constitutes a unique cohort in which to study early MPM biology.

#### 5.2 Rationale for the Meso-ORIGINS Feasibility Study

In a future study, called Meso-ORIGINS, we aim to define the key biological events that drive or permit evolution of MPM by recruiting a large population of patients with BAPE. According to the optimal (but most invasive) Meso-ORIGINS design, the study will utilise sequential LAT biopsies acquired over 2-year period preceding the development of MPM. These will facilitate unprecedented surveillance of the driving (oncological) and/or permissive (immunological) events involved in the development of MPM. The Meso-ORIGINS feasibility study will address important areas of uncertainty with regard to the current Meso-ORIGINS design, particularly the feasibility of the currently proposed surveillance protocol (involving LAT), patient acceptability and the sample size required (currently estimated at 850). Patient acceptance of alternative strategies for surveillance will be explored including imaging, blood tests for biomarkers (3, 4) and breath tests (5, 6, 7).

In a prospective element, the Meso-ORIGINS feasibility study will determine the technical feasibility of LAT based on TUS measurements. A Patient Acceptability Questionnaire will be used to determine patients' views on this and a range of less invasive alternative surveillance strategies. A retrospective cohort study using LAT/VAT and image guided pleural biopsy databases at each site will determine more precisely the subsequent incidence of MPM in patients diagnosed with BAPE. If the true MPM rate is lower than the 12% previously reported (2) this would mandate a larger, potentially unfeasible sample size

# 6 Patient Selection

#### 6.1 Inclusion Criteria

All study participants involved in either the Prospective Feasibility Study or the Retrospective Cohort Study will be subject to the following inclusion criteria:

- History of asbestos exposure or compatible radiology, e.g., pleural plaques
- CT imaging compatible with BAPE (which must include pleural effusion) or compatible histological diagnosis at biopsy including any of the following: benign fibrinous pleurisy, non-specific pleuritis or atypical mesothelial proliferation

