#### NB Histological confirmation is required for the Retrospective Cohort Study

Patients recruited to the Prospective Feasibility Study must also meet the following additional inclusion criteria:

- Informed written consent
- Expected prognosis  $\geq$  6 months

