#### 6.2 Exclusion Criteria

All study participants involved in either the Prospective Feasibility Study or the Retrospective Cohort Study will be subject to the following exclusion criteria:

- Histological diagnosis of MPM or any secondary pleural malignancy
- Diagnosis of pleural infection, empyema or granulomatous pleuritis

In addition, potential cases identified for the Retrospective Cohort Study must also be assessed against the following **additional exclusion criterion:** 

• < 2 years follow-up completed at the point of enrolment

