### 6.4 Retrospective Cohort Study Case Identification

Electronic databases will be used to identify cases meeting the study eligibility criteria. Existing databases in the trial centres involved contain data on approx. 1000 patients that have undergone LAT. These database should contain approx. 300 cases of BAPE based on previously published BAPE incidence of 30% in this population (2). Existing databases from VATS and image guided biopsy cases will also be used.

Cases can be entered throughout the period that the study is open. This includes cases diagnosed with BAPE with less than 2 years follow-up at the point the study opens, so long as 2 years follow-up has concluded by the time they are enrolled. The retrospective study will end after 12 months from opening and therefore patients who had a diagnosis of BAPE following LAT on or before 31/11/17 could be recruited.

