#### 6.6 Bias Reduction

In the retrospective study there is potential for recall and omission bias in data collection. We expect that this will be minimal as each centre that will be collecting data will have prospective databases where all LAT/VATS/image guided biopsies are recorded. In the prospective feasibility study there will be consecutive multicentre recruitment which will improve generalisation to a UK population. This is important as the data gathered will ultimately be used in the design of a future larger study.

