# 8 Retrospective Study Data Collection and Recording

The following data will be recorded retrospectively for all eligible patients using LAT/VAT/image guided biopsy databases and electronic health records at the study centres. A data collection form (.x/s) will be provided, including pre-populated study IDs. All data will be recorded in a linked anonymised format.

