# The date of BAPE diagnosis will be recorded. This is defined as the date on the pathology report describing features of BAPE that meet they eligibility criteria as explained in section 6.

Imaging, pleural fluid and blood results should be recorded at first presentation.

Cases can be entered throughout the period that the study is open. This includes cases diagnosed with BAPE with less than 2 years follow-up at the point the study opens, so long as 2 years follow-up has concluded by the time they are enrolled.

Demographics	Age*, Gender
Asbestos Exposure History	Occupational or environmental Nature of Occupation
CT Findings*	
 
Benign or Malignant Features
 
Based on previously reported criteria (5,11)
 
Calcified Pleural plaques
 
Present or Not Present
 

CXR appearance*	Effusion Laterality Effusion Size: • Small effusion (<50% thorax) • Large effusion (≥50% thorax)
Blood Tests*	Haemoglobin Neutrophils Lymphocytes Platelets CRP Albumin LDH Total Protein

Pleural Fluid	Total protein Albumin LDH Glucose Colour Cytology
LAT/VATS Findings	Date index procedure performed Were adequate views obtained? Which surfaces were abnormal? What was the nature of the abnormality/ies? • Smooth • Macro-nodular • Micro-nodular Number of biopsies Did the lung prove non-expansile (based on BTS criteria (≥50% re-apposition) (20) Did the subject have pleurodesis? Did the subject have an IPC placed? Histology, Cytology, Pleural Fluid Chemistry Results
Follow-up Data	Record any new pleural diagnosis since LAT/VATS Record whether MPM diagnoses within 2 years of index LAT/VATS date

\*at presentation

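### Retrospective cohort: the asbestos criterion does not say which records may establish it, so exposure first recorded after an MPM diagnosis could make a patient eligible and may bias the transition rate upward

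*Protocol*

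**What the plan says.** Protocol section 6.1 applies one asbestos criterion to both studies: "History of asbestos exposure or compatible radiology, e.g., pleural plaques". A note beneath it adds that "Histological confirmation is required for the Retrospective Cohort Study". Neither sentence says by when the exposure or the radiology must have been on record.

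The timing of retrospective entry is fixed. Section 6.2 excludes a case with "< 2 years follow-up completed at the point of enrolment", and section 6.4 admits recent diagnoses only "so long as 2 years follow-up has concluded by the time they are enrolled".

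Section 8 gives the source: "The following data will be recorded retrospectively for all eligible patients using LAT/VAT/image guided biopsy databases and electronic health records at the study centres". The follow-up items on the same form include whether MPM was diagnosed within 2 years. Section 8 dates the BAPE diagnosis by the pathology report and adds that "Imaging, pleural fluid and blood results should be recorded at first presentation". Age, CT, CXR and blood tests are marked as values at presentation. The asbestos item, "Occupational or environmental Nature of Occupation", carries no such mark and no date of documentation.

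Section 6.6 concedes that "In the retrospective study there is potential for recall and omission bias in data collection", but expects little of it because each centre logs its biopsies prospectively.

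**The concern.** The retrospective primary end-point (section 4.5.2) is the number of eligible patients with MPM within 2 years divided by the number of eligible patients. Eligibility therefore has to be decided on information that does not depend on the outcome.

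Take two patients with the same index record: non-specific pleuritis on biopsy, no exposure noted and no plaques. One develops MPM, has an occupational history taken during that work-up, and then meets 6.1. The other stays benign, is not asked again, and does not meet it. Nothing in the protocol prevents this. No date limit applies, no blinding of the person judging eligibility is stated, and the date of first documentation is not captured. The reassurance in section 6.6 concerns finding the biopsies, not finding the exposure.

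The rate exists to make the Meso-ORIGINS sample size more precise. The synopsis and section 5.2 both name a rate below 12% as the threat to feasibility. An upward bias would hide exactly that.

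**Working it through.** **1. The plan's own figures.**
- Section 5.1.3: 142 LAT patients × 31% = 44 with BAPE, and 12% of 44 is about 5 events. The stated interval of 4.5% to 26.4% is matched by 5/42 = 11.9% with the continuity-corrected Wilson method (4.47% to 26.43%). The denominator of 42 is inferred, not stated.
- Main study: 850 × 0.12 = 102, in line with the stated 100 MPM cases. Conversely 100 / 0.12 = 833.3, so 834.
- Retrospective target: 1000 × 0.30 = 300.
- Recruitment (section 4.4.2): 850 / (25 centres × 5 years) = 6.8 per centre per year.

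**2. Direction.** A patient who qualifies only through exposure found in an MPM work-up adds 1 to both numerator and denominator. Any rate below 100% then rises. Near 36/300, one such case is worth 36/300 − 35/299 = 12.0% − 11.7%, about 0.3 percentage points.

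Patients who stay benign can also be documented late. Let k of the 36 MPM cases and m of the 264 others qualify only on later records. The rate on index information is

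(36 − k) / (300 − k − m).

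This equals 12% when k/36 = m/264. For k = 6 that needs m = 44: 30/250 = 12.0%. So the bias is upward only if the late fraction is larger among MPM cases. With equal fractions there is no bias.

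**3. Size, by assumption.** No passage gives k or m. Take 300 enrolled with 36 MPM (12.0%, exact 95% CI 8.5% to 16.2%) and set m = 0. N for 100 MPM cases is 100 divided by the rate. The last column is N / 125.

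| k (assumed) | Rate on index information | N for 100 MPM | MPM cases in 850 | Patients per centre per year |
|---|---|---|---|---|
| 0 | 36/300 = 12.0% | 834 | 102.0 | 6.67 |
| 3 | 33/297 = 11.1% | 900 | 94.4 | 7.20 |
| 6 | 30/294 = 10.2% | 980 | 86.7 | 7.84 |
| 12 | 24/288 = 8.3% | 1200 | 70.8 | 9.60 |

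Setting m = 0 is the least favourable case for each k. Any late documentation among benign patients shrinks the shift.

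**4. The two limbs of the criterion.** Section 8 takes CT findings, calcified plaques included, from presentation. A patient with plaques on that scan qualifies whatever is learned later. Section 6.1 does not require the qualifying radiology to be that scan, so this limb is only partly protected. The history limb has no anchor at all.

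**The case against.** The strongest reply is that section 6 describes status at the index diagnosis. The exclusion for histological MPM is undated too, and applied at enrolment it would remove every histologically confirmed transition from the numerator. The shared criteria must therefore look back to the index date. That reading is sound, but it does not close the gap. Exposure decades ago is a fixed fact, so exposure first written down during an MPM work-up is still true at index. What remains open is which records may prove it.

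Three further points stand and limit the finding:
- No passage says that MPM patients are questioned again or that benign patients are not. Section 5.1.3 has BAPE patients routinely followed in pleural clinics, so benign patients may also be documented late.
- The missing mark beside asbestos history is weak evidence of intent. The marks fall on values that change over time, and gender has none either.
- Only patients with neither plaques nor a recorded history at index can be affected.

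A reader might infer that the rate is certainly inflated, and perhaps greatly. For example, if all MPM cases but only 60% of the others were documented as exposed, 36 / (36 + 0.6 × 264) = 36/194.4 = 18.5%. The documents do not support this. If index documentation were 60% in both groups, 40% of MPM cases (14.4 of 36) would have had no qualifying record at index, and nothing suggests that.

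It can also be said that a sensitivity analysis belongs in a SAP, which is not shown. That is true, but who is eligible and on what evidence is protocol content.

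**Conclusion.** The point holds as a conditional risk. As written, the plan lets records created because of the outcome decide who enters the denominator of the retrospective primary end-point, and section 6.6 does not address it. The bias is upward if late documentation is more common, as a fraction, in MPM than in benign patients, and absent if it is equally common.

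The size cannot be derived from the documents. Under the assumed 3 to 12 late-qualifying cases out of 36, with none among benign patients, an observed 12.0% stands for 11.1% to 8.3%, and the size needed for 100 MPM cases is 900 to 1200 rather than 834. The shifts at 3 and 6 cases stay within the exact interval for 36/300, and 12 cases falls just below its lower limit of 8.5%. Unlike sampling error, though, such a shift would not shrink with more cases and would not show in the interval. The change is worth making because it is cheap, not because a large bias has been shown.

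**What to change.** In section 6.1, for the Retrospective Cohort Study only, require asbestos exposure or compatible radiology to be established from records or imaging dated on or before the index BAPE pathology report, or from the first clinic visit after that biopsy. The second option matches the prospective study, where Visit 1 takes the exposure history.

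In section 8, add a yes/no field for whether the qualifying evidence was documented by that date.

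Exclude cases that qualify only on later information from the primary rate, and report the rate with them included as a sensitivity result. The difference between the two rates shows how much the issue mattered.

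The cost is one sentence and one field. A few truly exposed patients whose exposure was written down late leave the denominator, which slightly reduces the number available towards 300.

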#### NB Histological confirmation is required for the Retrospective Cohort Study

Patients recruited to the Prospective Feasibility Study must also meet the following additional inclusion criteria:

- Informed written consent
- Expected prognosis  $\geq$  6 months

#### 6.2 Exclusion Criteria

All study participants involved in either the Prospective Feasibility Study or the Retrospective Cohort Study will be subject to the following exclusion criteria:

- Histological diagnosis of MPM or any secondary pleural malignancy
- Diagnosis of pleural infection, empyema or granulomatous pleuritis

In addition, potential cases identified for the Retrospective Cohort Study must also be assessed against the following **additional exclusion criterion:** 

• < 2 years follow-up completed at the point of enrolment

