#### **10.2.2** Retrospective Cohort Study

Results will be reported using simple descriptive statistics. The **primary end-point** shall be the rate of MPM transition. This will be calculated by dividing the number of eligible patients diagnosed with MPM within 2 years of the index diagnosis of BAPE by the total number of eligible patients. The **secondary end-point** shall be based on the content of a logistic regression model for MPM transition generated using baseline data as candidate predictors.

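### The malignancy exclusion in section 6.2 has no date, so it does not separate disease present at the index BAPE diagnosis from the later MPM that the retrospective cohort counts

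*Protocol*

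**What the plan says.** Protocol section 6.2 opens with criteria shared by everyone in the "Prospective Feasibility Study or the Retrospective Cohort Study will be subject to the following exclusion criteria". The first is "Histological diagnosis of MPM or any secondary pleural malignancy". It carries no date. A separate bullet, for the retrospective cohort only, excludes cases with "< 2 years follow-up completed at the point of enrolment". Section 6.4 likewise admits more recent cases "so long as 2 years follow-up has concluded by the time they are enrolled".

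The retrospective primary end-point in section 4.5.2 is "the number of eligible patients diagnosed with MPM within 2 years of the index diagnosis of BAPE divided by the total number of eligible patients". Section 10.2.2 repeats it. Eligibility therefore governs both numerator and denominator.

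Section 8 takes the BAPE date from the pathology report whose findings satisfy section 6. It also asks sites to record any new pleural diagnosis, and whether MPM was diagnosed within two years of the index LAT or VATS date. Pleural fluid cytology is among the items collected. The synopsis cell with the exclusion criteria is damaged in the text available, but it appears to name both histology and cytology, again without a date.

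**The concern.** Eligibility for the retrospective cohort is judged after the outcome window has closed, by a criterion that names the outcome. If a site reads the rule as applying to everything in the record, a histologically confirmed transition is ineligible and leaves both numerator and denominator. A secondary pleural malignancy found after the index biopsy can also be dropped in apparent compliance, which shrinks the denominator. MPM on an early repeat biopsy is the hardest case. Section 5.1.3 itself raises the possibility that some BAPE reflects a false negative biopsy, so one site might exclude such a patient and another count a transition.

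The histology-only wording raises a second, separate question. A patient with a benign biopsy but MPM on cytology from the index procedure stays eligible under section 6.2 and could be counted as a transition, although the disease was already present.

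The rate drives the size of the main study. The synopsis warns that a true rate near 4.5% may make that study unfeasible, so a downward bias could mislead the decision. It would also be hard to see: sections 6.3 and 7.2 describe medical review of eligibility and a screening log for the prospective study, and nothing similar is described for retrospective cases.

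**Working it through.** **Inputs.** Expected two-year rate 12%, 95% CI 4.5% to 26.4% (section 5.1.3); target 300 and four named centres (section 10.1.2); 850 patients giving about 100 MPM cases (section 4.1).

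**The plan's own figures.** 142 × 0.31 = 44 BAPE patients in the earlier study. The protocol gives no event count. 5/42 = 11.9% with a continuity-corrected Wilson interval gives 4.5% to 26.4%, which matches, but 5/42 is inferred. 850 × 0.12 = 102, consistent with about 100. For exactly 100 cases, 100/0.12 = 833.

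**Exclusion judged at index.** 300 × 0.12 = 36 expected MPM cases. 36/300 = 12.0% (Clopper-Pearson 95% CI 8.5% to 16.2%).

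**MPM cases dropped at enrolment.** If d cases are excluded, the rate is (36 − d)/(300 − d). Assume four equal centres (75 patients and 9 MPM cases each) and histological confirmation of every MPM case:

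| Centres applying the rule literally | Rate |
|---|---|
| 0 | 36/300 = 12.0% |
| 1 | 27/291 = 9.3% |
| 2 | 18/282 = 6.4% |
| 3 | 9/273 = 3.3% |
| 4 | 0/264 = 0% (upper 95% limit 1.4%) |

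With one such centre, the number needed for 100 MPM cases becomes 100/(27/291) = 1,078 instead of 833.

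**Sensitivity to the true rate, one centre.** The rate becomes 0.75p/(1 − 0.25p). At p = 4.5%: 0.03375/0.98875 = 3.4%. At p = 26.4%: 0.198/0.934 = 21.2%.

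**Sensitivity to the histological share.** Only histological MPM meets the exclusion, so a lower share removes fewer cases. With all four centres literal, a share of 90% gives 4/268 = 1.5%, 80% gives 7/271 = 2.6%, and 50% gives 18/282 = 6.4%. With one centre and 80% (about 7 of its 9 cases), the rate is 29/293 = 9.9%.

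**Later secondary malignancy dropped.** The rate is 36/(300 − s). The documents give no frequency, so s is assumed: 2% (6 patients) gives 36/294 = 12.2%, 5% (15) gives 36/285 = 12.6%, and 10% (30) gives 36/270 = 13.3%.

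**MPM on index cytology counted as a transition.** Each such patient added to the cohort adds one to numerator and denominator; one patient gives 37/301 = 12.3%. The documents give no frequency. Section 5.1.2 says that cytology performs poorly in MPM, so the group is probably small.

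**The case against.** The strongest reply is that, read as a whole, the protocol already means malignancy at index. The end-point counts eligible patients who later develop MPM, and it would be close to empty if later MPM made them ineligible. Section 8 links the BAPE date to a pathology report satisfying section 6, and its form asks for later pleural diagnoses. A site completing that form could hardly treat every later MPM as an exclusion. This stands as evidence of intent, and it rules out presenting 0/264 as what will happen.

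Two inferences that a reader might draw also fail. The words about the point of enrolment belong to the follow-up bullet and do not date the malignancy exclusion. And the histology-only wording does not cause the loss of MPM cases. It limits the loss, because MPM diagnosed by cytology or clinically would remain.

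It is also fair that malignant index cytology would not automatically count as a transition. Secondary malignancy would only enlarge the denominator, and the numerator needs an MPM diagnosis.

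The reply leaves a gap, however. No passage expressly dates the exclusion, and the implied intent does not settle what to do with early repeat-biopsy MPM or with later secondary malignancy, which the rule names and which is not the outcome.

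**Conclusion.** The point holds as a drafting gap in section 6.2 that should be closed, because the primary rate depends on it. It is not shown that the design as intended biases the rate, and the documents do not support the stronger reading that the exclusion will empty the numerator.

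The size depends on how sites apply the rule. One literal centre out of four would lower the estimate by 12.0 − 9.3 = 2.7 percentage points. That is within the 3.5 points between 12.0% and its lower confidence limit of 8.5%, but it is systematic and would not shrink with more patients. Dropping later secondary malignancies in 5% of patients would raise it by 0.6 points. The equal centres, the number applying the rule literally, full histological confirmation and the 5% are all assumptions. The cytology mismatch is a smaller, separate matter, and it rests partly on a damaged synopsis cell.

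**What to change.** In section 6.2 and the synopsis:

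- Exclude histological or cytological MPM or secondary pleural malignancy established on or before the index diagnosis (retrospective study) or before consent (prospective study). For the retrospective study, include any sample taken at or before the index procedure, even if it was reported later. Otherwise index cytology reported after the biopsy would be taken for an outcome.
- State that in the retrospective study, malignancy diagnosed from later samples is follow-up data and not grounds for exclusion, with MPM within two years as the outcome.
- Use one index date throughout. Section 8 uses the pathology report date in one place and the LAT or VATS date in another, and the second does not fit the image-guided biopsy cases that section 6.4 also admits.

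The cost is two sentences plus the alignment of the index date. No new data are needed, since cytology, the index dates and later diagnoses are already collected.
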